- *Panel assessed cosmetic outcome*: in addition to patient self-reported and physician reported outcomes, cosmesis will be assessed by a panel of breast cancer medical providers using digital photographs from baseline and at 2 years. The Panel will be blinded to treatment allocation.

- *IBTR*: this is defined as local recurrence from trial registration as a first event at 5 years. IBTR is defined as both invasive and non-invasive breast cancer involving the same breast parenchyma as the original tumor.
- *Regional recurrence*: invasive breast cancer in the axilla, regional lymph nodes, chest wall, and skin of the ipsilateral breast at 5 years.
- *Distant recurrence*: metastatic cancer that has either been biopsy confirmed or clinically diagnosed as recurrent invasive breast cancer at 5 years.
- *Invasive disease free survival*: this is defined as the time from study registration until the occurrence of one of the events in a composite endpoint. This endpoint includes invasive IBTR, regional invasive breast cancer recurrence, distant breast cancer recurrence, death due to any cause, contralateral invasive breast cancer, and second primary non-breast invasive disease.
- *Overall survival*: is defined as the time from registration to death due to any cause.

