16.62 Secondary Analyses

16.621 *Acute adverse events (up to 90 days post-RT):* All patients who were registered to the study and started treatment will be included in the acute adverse event analysis. An acute adverse event is an AE, regardless of attribution, that occurs up to 90 days post-RT. The maximum grade for each type of acute AE will be recorded for each patient. Data will be summarized as frequencies and relative frequencies by treatment arm. Additionally, the relationship of the adverse event(s) to the study treatment will be taken into consideration.

16.622 *Late adverse events and reconstruction failure:* All patients who were registered to the study and started treatment will be included in the late adverse event and reconstruction failure analysis. A late adverse event is an AE, regardless of attribution, that occurs at least 90 days post-RT and up to 5 years post-RT. The maximum grade for each type of late AE will be recorded for each patient. Data will be summarized as frequencies and

relative frequencies by treatment arm. Additionally, the relationship of the adverse event(s) to the study treatment will be taken into consideration.

- 16.623 *Quality of life*: The subscales of the BCTOS, elements from CTCAE-PRO, and other patient reported measures such as fatigue, breast pain, breast shape, and arm related morbidity outlined in the appendix will be summarized as the mean \pm SD and median (minimum value, maximum value). Changes in the QOL measurements from baseline will be determined at each follow-up visit and measured by treatment arm. The comparison of the changes at each time point between the two treatment arms within each cohort will be done with a paired t-test or Wilcoxon signed rank test, whichever is appropriate.
- 16.624 *Cosmesis*: The values of the cosmesis instruments (patient self-reported and panel-assessed) will be summarized with the frequencies and confidence intervals of fair or poor cosmesis events at baseline, 2 years, and 5 years by treatment arm.
- 16.625 *IBTR incidence*: The IBTR cumulative incidence will be estimated using a competing risks method (Gooley et al.) by treatment arm. The competing risks will be regional/distant breast cancer recurrence and death.

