- 16.626 *Regional recurrence incidence*: The regional breast cancer recurrence cumulative incidence will be estimated using a competing risks method (Gooley et al.) by treatment arm. The competing risks will be local/distant breast cancer recurrence and death.
- 16.627 *Distant recurrence incidence*: The distant breast cancer recurrence cumulative incidence will be estimated using a competing risks method (Gooley et al.) by treatment arm. The competing risks will be local/regional breast cancer recurrence and death.
- 16.628 *Disease-free survival*: DFS is defined as the time from registration until the time of disease recurrence or death due to any cause. The DFS will be estimated with a Kaplan-Meier estimator and curve by treatment arm. Estimates will be given for specific time points along with 95% CIs.
- 16.629 *Overall survival*: The OS will be estimated with a Kaplan-Meier estimator and curve by treatment arm. Estimates will be given for specific time points along with 95% CIs.
- 16.63 Exploratory Analyses: 2D and 3D strain parameters will be analyzed after radiotherapy compared to baseline and will be compared between patients undergoing conventional versus hypoofractionated radiotherapy. Continuous variable will be compared using unpaired t tests and nominal variables will be compared using contingency tables and Chi square analyses.
- 16.64 Correlative Analyses:

16.641 Cardiac toxicity

Cardiac toxicity remains an important late effect of radiotherapy for breast cancer.[3, 34, 37, 38] Echocardiography is a noninvasive tool that enables the detection of cardiovascular disease as a result of radiotherapy. Echocardiography can detect pericardial disease, left ventricular systolic and diastolic dysfunction, coronary artery disease suggested by resting or stress-induced regional wall motion abnormalities, and valvular heart disease.[33] Ideally, cardiac toxicity could be predicted prior to the onset of clinical symptoms to enable an earlier opportunity for risk stratification, surveillance, and preventative interventions that reduce risk. Echocardiographic strain rate imaging, a measure of regional myocardial function, has previously been reported to detect subclinical decline in cardiac function in the anterior wall of patients treated with radiotherapy for left-sided breast cancer.[34]

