18.0 Records and Data Collection Procedures

18.1 Submission Timetable

Initial Material(s) -

CRF	Treatment (Compliance with Test Schedule Section 4.0)
Institutional Contacts	
Patient Eligibility	
Demographics	
On-Study	≤2 weeks after registration
On Study: Neoadjuvant Chemotherapy	
Surgery	
Pathology of Ipsilateral Breast	
Breast Reconstruction	
Adjuvant Therapy	
Adverse Events- Baseline	
Specimen Submission: Blood (Baseline)	
Specimen Submission: Tissue (Baseline)*	*6 months after accrual

CRF	Treatment (Compliance with Test Schedule Section 4.0)
Patient Status: Baseline	
Patient Assessment	
Off Treatment	Submit ≤2 weeks after registration if withdrawal/refusal occurs prior to beginning protocol therapy

Test Schedule Material(s)

CRF	End of Treatment	12 weeks post/Observation Phase ⁴	Event Monitoring ⁵
Radiation Therapy	X		
Post Mastectomy Therapy: Chest Wall	X		
Radiation Therapy: Regional Nodes	X		
Patient Assessment	X	X	
Specimen Submission: Blood (post rad tx)	X		
Adverse Events Solicited	X	X	
Adverse Events: Other	X ²	X ²	
Off Treatment	X ²	X ²	
Patient Status Form	X	X	X
Specimen Submission: Tissue (Recurrence)		X ²	
Consent Withdrawal	X ²	X ²	
Lost to Follow-up	X ²	X ²	
Breast/Chest Wall Radiotherapy Questionnaire ³	X	X	

1. Complete at each evaluation during Active Treatment (see Section 4.0).
2. When applicable
3. Survey will need to be entered manually if has not alternately been scanned or entered electronically
4. Active monitoring observation phase, post radiation (+/- 2 days), 12 weeks (+/- 4 weeks), 12 months (+/- 30 days), annually for 4 years (+/- 3 months, total 5 years follow-up). If patient progresses within observation, they will move to the event monitoring phase where they will be followed until 5 years of follow-up information has been completed from the end of treatment timepoint
5. If patient has a recurrence prior to being off radiation therapy for 5 years, continue to follow yearly.

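### Sections 16.626 and 16.627 estimate regional-first and distant-first recurrence, while section 16.2 defines both endpoints without a first-event limit

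*Combined protocol and SAP*

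**What the plan says.** **Definitions (section 16.2).**
- IBTR carries a first-event limit: "this is defined as local recurrence from trial registration as a first event at 5 years".
- Regional recurrence does not: "invasive breast cancer in the axilla, regional lymph nodes, chest wall, and skin of the ipsilateral breast at 5 years".
- Distant recurrence does not: "metastatic cancer that has either been biopsy confirmed or clinically diagnosed as recurrent invasive breast cancer at 5 years".

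**Analyses (section 16.62).** For all three, "cumulative incidence will be estimated using a competing risks method (Gooley et al.) by treatment arm". The competing events are:
- IBTR (16.625): "The competing risks will be regional/distant breast cancer recurrence and death".
- Regional (16.626): "The competing risks will be local/distant breast cancer recurrence and death".
- Distant (16.627): "The competing risks will be local/regional breast cancer recurrence and death".

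**Follow-up after a recurrence.** Section 13.1 moves the patient to event monitoring, and note 5 of section 18.1 adds: "If patient has a recurrence prior to being off radiation therapy for 5 years, continue to follow yearly". Section 11.2.3 collects the site of recurrence as local, regional or distant.

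**The concern.** In a cumulative incidence analysis a patient leaves the risk set at her first listed event. If that event is a chest-wall or nodal recurrence, a later metastasis cannot enter the distant curve. If it is a metastasis, a later nodal recurrence cannot enter the regional curve. Neither later event is excluded by section 16.2. A reader given a 5-year distant recurrence rate would thus receive the rate of distant disease as first failure, without being told.

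The dropped events depend on how often the other sites fail first. Other things equal, the arm with more locoregional failure loses more distant events. The plan also has no rule for recurrences found at two sites on the same date, where each site is listed as the other's competing event.

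**Working it through.** **1. Definition against analysis.**

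| Endpoint | First-event limit in 16.2 | Competing events in 16.62 | Agree? |
|---|---|---|---|
| IBTR | Yes | Regional, distant, death | Yes |
| Regional | No | Local, distant, death | No |
| Distant | No | Local, regional, death | No |

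**2. Does another analysis recover the later events?** No. Disease-free survival (16.628) and invasive disease-free survival (16.2) stop at the first event, and overall survival (16.629) counts only deaths.

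**3. Direction.** Incidence as defined = incidence as first failure + incidence after another recurrence. The last term cannot be negative, so 16.626 and 16.627 can only equal or understate the incidence as defined.

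**4. Size for distant recurrence (illustration).** The plan states no recurrence rate, so there is no figure of its own to reproduce. The only input from the documents is arm size: section 16.4 plans to treat 82 patients, 1:1, so 82/2 = 41 per arm. The rest are assumptions, each a 5-year risk taken alone with a constant hazard:
- first locoregional recurrence: 5% or 10%
- distant recurrence as first event: 10% or 20%
- distant recurrence within 5 years after a locoregional recurrence: 30% or 60%
- death without recurrence: 3% (the same death hazard is applied after locoregional recurrence)

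Each risk r becomes a yearly hazard −ln(1 − r)/5. Write hL, hD, hP and hM for the four in that order, with H = hL + hD + hM, K = hP + hM, A = (1 − e^(−5K))/K and B = (1 − e^(−5H))/H. Then:
- counted under 16.627: hD × B
- missed under 16.627: hP × hL × (A − B)/(H − K)

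Worked case (10%, 10%, 60%, 3%): hL = hD = 0.02107, hP = 0.18326, hM = 0.00609, H = 0.04824, K = 0.18935, A = 3.232, B = 4.443.
- Counted: 0.02107 × 4.443 = 9.36%.
- Missed: 0.18326 × 0.02107 × (3.232 − 4.443)/(0.04824 − 0.18935) = 3.31%.
- As defined: 9.36 + 3.31 = 12.67%. The missed share is 3.31/12.67 = 26%.

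All eight combinations:

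| Locoregional first | Distant first | Distant after locoregional | Counted by 16.627 | As defined in 16.2 | Missed (points) | Women per 41 |
|---|---|---|---|---|---|---|
| 5% | 10% | 30% | 9.61% | 10.37% | 0.76 | 0.31 |
| 5% | 10% | 60% | 9.61% | 11.25% | 1.64 | 0.67 |
| 5% | 20% | 30% | 19.23% | 19.96% | 0.73 | 0.30 |
| 5% | 20% | 60% | 19.23% | 20.81% | 1.58 | 0.65 |
| 10% | 10% | 30% | 9.36% | 10.89% | 1.53 | 0.63 |
| 10% | 10% | 60% | 9.36% | 12.67% | 3.31 | 1.36 |
| 10% | 20% | 30% | 18.75% | 20.22% | 1.47 | 0.60 |
| 10% | 20% | 60% | 18.75% | 21.93% | 3.18 | 1.30 |

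The shortfall is 0.7-3.3 points, or 4-26% of all distant recurrences.

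**5. Between arms.** With 5% against 10% locoregional recurrence and the other inputs equal (10% and 60%), the arms lose 1.64 and 3.31 points. The difference is 3.31 − 1.64 = 1.67 points, about 0.7 of a woman in 41.

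**6. Regional recurrence.** The size was not calculated. Section 16.2 places chest-wall disease under regional recurrence and reserves IBTR for breast parenchyma, so in this post-mastectomy trial the regional events lost would mainly be those found after a metastasis.

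**The case against.** The strongest reply is that 16.625 to 16.627 form a coherent set. Each site is the event in turn, with the other sites and death competing, which splits first failures into mutually exclusive parts. That is a legitimate estimand, and in a first-failure analysis a recurrence elsewhere is a proper competing event even though it does not prevent metastasis. Adding a first-event limit to two definitions would also reconcile the text. This stands as far as it goes: the fault is the mismatch, not the method. But section 16.2 uses the first-event limit for one endpoint and omits it for the two beside it, and nothing tells the reader that those two rates are first-failure rates.

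It is also fair that these are secondary estimates by arm with no test or decision rule. With 41 women, an incidence of 15% has a 95% interval of about ±1.96 × √(0.15 × 0.85/41) = ±11 points, well above the shortfall.

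Three stronger readings are tempting, and the documents do not support them:
- A reader might infer that the analysis hides harm in the 15-fraction arm. Excess chest-wall or nodal failure as first event would itself appear in 16.626 and in disease-free survival, and resulting deaths in overall survival.
- A reader might multiply a locoregional rate by the share later metastatic: 4% × 40% = 1.6 points up to 12% × 60% = 7.2 points. If those shares are 5-year risks after recurrence, this ignores the time left before year 5. With recurrences spread evenly and constant hazard, the share reached is 1 − p/(−ln(1 − p)), or 22% for p = 40% and 35% for p = 60%. The range falls to 0.9-4.1 points.
- A reader might assume that dates of later recurrences are already in hand. Section 11.2 collects site and the date of first retreatment. In event monitoring the section 18.1 table marks only the Patient Status Form, whose contents are not given. Collection is implied, not stated.

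**Conclusion.** The point holds as a mismatch between definition and analysis with a known direction. Sections 16.626 and 16.627 give first-failure incidence, which cannot exceed and may understate the incidence defined in section 16.2. The size, 0.7-3.3 points for distant recurrence, rests wholly on assumed rates and constant hazards. The primary endpoint, sample size and stopping rule are untouched. It is worth correcting because the resulting rates would carry a label that does not match what they measure, and because the change is small.

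**What to change.** - In 16.626 and 16.627, count the first regional (or distant) recurrence by 5 years whenever it occurs, with death without that recurrence as the only competing risk.
- Count recurrences found simultaneously at several sites in each category.
- Keep the present analysis as a separate table, labelled as site of first failure.
- Confirm that the Patient Status Form used in event monitoring records the site and date of later recurrences, and add those items if it does not.

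**Cost.** SAP wording, and possibly a form change. Reported rates may be slightly higher. Regional recurrences after metastasis may be under-ascertained, because no examinations are scheduled in event monitoring; the report should say so. If the sponsor prefers the first-failure estimand, the minimum is to add the first-event limit to both definitions, label the results accordingly and state a rule for simultaneous sites. Metastases after a locoregional recurrence would then remain unreported.

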2.2.3 To determine the 5-year locoregional control, disease free survival and overall survival

- 2.24 To evaluate fatigue, arm function, and other patient reported outcomes
- 2.25 To evaluate clinical features, treatment technique, dose-volume parameters, histologic and genetic variants associated with fair and poor cosmetic outcome or unplanned surgical intervention.
- 2.26 To compare echocardiographic changes, including left ventricular strain pattern, between fractionation regimens

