4.0 Test Schedule

Assessments, tests and procedures	Treatment			Observation ⁷
	Baseline ²	Last day of treatment (+/- 2 days)	12 weeks (+/- 8 weeks) post-radiation	12 months (+/- 3 month) post completion of radiotherapy, 24 months (+/- 3 months), 36 months (+/- 3 months), and at 5 years (+/- 3 months)
History and Physical exam (including breast assessment/exam) ¹	X	X	X	X
Mammogram	X ¹⁰			X ¹¹
Cosmesis ,QOL Outcome Assessment and Breast-Q ¹⁶ (see section 11.3 and Appendix)	X ¹³	X	X	X
Digital Photograph	X	X	X	X
Review of surgical specimen(s) to confirm eligibility	X ³			
Echocardiography ^{9, 14}	X ¹³			X ⁸
Radiation toxicity assessment (see section 10.4)	X	X	X	X
Serum pregnancy test	X ⁴			
Blood specimen ^{5, 17, R}	X ¹⁵	X	X	X ¹²
Surgical tumor specimen ^{6, 18, R}	X			

1. A general history & physical must be done \leq 8 weeks prior to registration. This should include an assessment of ECOG performance status (see Appendix I).

2. Following definitive surgical resection and adjuvant chemotherapy if indicated, prior to the start of radiation.
3. Outside pathology must be reviewed at the treating institution.
4. For women of childbearing potential only, must be within 7 days of radiotherapy
5. See section 14 for collection time and preparation of samples
6. See section 17 for collection time and preparation of samples
7. Patients that cannot come back to Mayo Rochester within the time constraints of the follow-up schedule; efforts to obtain outside records and send QOL's to be completed will occur, however the required items may not be captured.
8. Ideally 6-12 months post radiotherapy in HER2 positive patients treated with HER2 directed therapy and in patients treated with anthracycline as part of routine clinical care. Only followed for Echos 1 year post therapy.
9. Co-enrollment on IRB 15-007443 (echo protocol) is required in Rochester while open
10. Completed \leq 12 months prior to study entry
11. As clinically indicated
12. At 12 months post-treatment visit only to coincide with echocardiography.
13. Should be \geq 14 days since last chemotherapy
14. After closure of IRB 15-007443 (echo protocol) echocardiography tests will be performed only in left sided patients previously treated with anthracycline and/or HER2 directed systemic therapy. This correlative component will occur at Rochester Mayo only.
15. Baseline blood collection will be drawn through co-enrollment on IRB 15-000136 (Radiation Oncology Outcomes Registry and Biobanking Study).

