16.4 Sample Size Determination

The proposed trial design is a randomized phase II trial with a 1:1 randomization ratio with the stratification variable noted in section 5.1. The primary endpoint for this trial is the 24-month complication rate, as defined above. The study will plan to enroll a total of 72 evaluable patients. An evaluable patient is defined as a patient who receives any dose of the protocol-defined radiotherapy. In this trial, we will accrue and randomize up to 96 patients over 3 years to account for ineligibility, cancellations (withdrawals prior to protocol therapy), major treatment violations, or other reasons, and treat a total of 82 patients in order to ensure 72 evaluable patients at 24 months.

This study is designed as a non-inferiority/superiority “hybrid” design using the approach of Freidlin et al.[36] It is estimated that approximately 2/3 of the patients will undergo reconstruction. For patients who undergo mastectomy with immediate reconstruction, the rate of unplanned surgical complications at the Mayo Clinic is ~15% (personal communications with [name] and [name] 6/2014), comparable to what has been reported in the literature in the modern era.[27]. The rate of grade 3 or greater late toxicity in this population is expected to be $\leq 1\%$ (Whelan ASCO 2011). For the purpose of designing this trial, we will assume a 10% complication rate in the control arm. We consider that a 10% increase of this rate in the experimental arm would be acceptable (i.e. a non-inferiority margin of 10%). Based on the results of the START-B clinical trial[9], it is also plausible that toxicities in the experimental arm may even be reduced with the shortened fractionation schedule. Therefore, a marginal *decrease* in complication rate in the experimental arm to 5% (i.e. marginal benefit margin of 5%) may be reasonably expected. Denote p_0 and p_1 as the 24-month complication rate in the control arm and experimental arm, respectively. The null hypothesis is that the complication rate in the experimental arm is inferior to the control rate of 10% by more than 10% (i.e. $H_0: p_1 - p_0 > 10\%$). The alternative hypothesis is that the complication rate in the experimental arm is non-inferior to the control rate of 10% (i.e. $H_A: p_1 - p_0 < 10\%$).

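### Section 16.63 names only independent-sample tests for echocardiography, leaving the before/after comparison without a suitable test and the between-arm analysis variable unstated

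*Combined protocol and SAP*

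**What the plan says.** Goal 2.26, listed among the secondary goals, is "To compare echocardiographic changes, including left ventricular strain pattern, between fractionation regimens". The matching analysis is section 16.63, headed exploratory, which states: "2D and 3D strain parameters will be analyzed after radiotherapy compared to baseline and will be compared between patients undergoing conventional versus hypoofractionated radiotherapy". The next sentence holds the only methods named: "Continuous variable will be compared using unpaired t tests and nominal variables will be compared using contingency tables and Chi square analyses". No paired test, change score or baseline covariate is mentioned.

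The test schedule (section 4.0) has an echocardiogram at baseline and another after radiotherapy, with echo follow-up ending at one year. Both measurements therefore come from the same patient.

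The echo sample is smaller than the trial. Section 16.4 says "The study will plan to enroll a total of 72 evaluable patients", in "a randomized phase II trial with a 1:1 randomization ratio". Footnote 14 to the schedule says that once the companion echo protocol closes, "echocardiography tests will be performed only in left sided patients previously treated with anthracycline and/or HER2 directed systemic therapy", and adds "This correlative component will occur at Rochester Mayo only". No sample size, standard deviation, target difference or significance level is given for the echo analysis.

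**The concern.** Two different contrasts are announced and one family of tests follows. An unpaired t test or an ordinary chi-square test treats the two sets of values as coming from different people. That is right for arm against arm. It is wrong for baseline against follow-up in the same patients, where the pairing carries most of the information.

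The question is about toxicity: has cardiac function declined? A test that is too insensitive errs towards reporting no decline.

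Between arms the issue is under-specification. The text is compatible with a comparison of post-radiotherapy values, of change scores, or of baseline-adjusted values. These can give different answers, and nothing fixes the choice before the data are seen. The echo subset is small, so the lost precision matters too.

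**Working it through.** The plan gives no echo figure to reproduce. The check is therefore how much the choice of test matters.

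**Inputs.** From the documents: at most 72 evaluable patients, 1:1, so 36 per arm. Assumed: equal SD (set to 1) at baseline and follow-up; correlation r between 0.3 and 0.8; a before/after shift of 0.3 SD; a between-arm difference of 0.5 SD; a two-sided 5% level; and 36 patients (18 per arm) as an illustrative echo subset.

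**Before/after, n patients.**
- Unpaired variance of the mean difference: 2/n. Paired variance: 2(1-r)/n.
- Ratio of standard errors, unpaired to paired: 1/sqrt(1-r).
- True type I error of the unpaired test at nominal 5% (normal approximation): 2[1 - Φ(1.96/sqrt(1-r))].

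| r | SE ratio | True type I error |
|---|---|---|
| 0.3 | 1.20 | 1.9% |
| 0.5 | 1.41 | 0.6% |
| 0.7 | 1.83 | 0.03% |
| 0.8 | 2.24 | <0.01% |

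Simulation with t tests (20,000 runs, 18 or 36 pairs) gave about 0.8% at r = 0.5 and 0.05% to 0.08% at r = 0.7. The paired test stayed at 4.8% to 5.1%.

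Power for a 0.3 SD shift at r = 0.7:
- 36 patients, unpaired: Φ[(0.3/sqrt(2/36) - 1.96)/sqrt(0.3)] = Φ[(1.273 - 1.96)/0.548] = 11%.
- 36 patients, paired: Φ[0.3/sqrt(0.6/36) - 1.96] = Φ[2.324 - 1.96] = 64%.
- 72 patients, same formulas: 39% unpaired, 91% paired.

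**Between arms: validity.** With 18 or 36 per arm and r = 0.5 or 0.7, the simulated type I error of the unpaired t test was 5.0% to 5.2% on post values and 4.9% to 5.1% on change scores. The standard errors are correct in both cases.

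**Between arms: precision.** Variance relative to a post-only comparison is 1 for post-only, 2(1-r) for change scores and 1-r² for ANCOVA (ignoring the small cost of estimating the slope). ANCOVA relative to change scores is (1-r²)/[2(1-r)] = (1+r)/2.

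| r | Change / post-only | ANCOVA / post-only | ANCOVA / change |
|---|---|---|---|
| 0.5 | 1.00 | 0.75 | 0.75 |
| 0.7 | 0.60 | 0.51 | 0.85 |

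Power for a 0.5 SD difference:

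| Per arm | r | Post-only | Change | ANCOVA |
|---|---|---|---|---|
| 18 | 0.5 | 32% | 32% | 41% |
| 18 | 0.7 | 32% | 49% | 56% |
| 36 | 0.5 | 56% | 56% | 69% |
| 36 | 0.7 | 56% | 78% | 84% |

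**The case against.** The best defence is that section 16.63 describes one analysis, not two. Strain is analysed relative to baseline, and that change is then compared between arms. Goal 2.26 supports this, since it targets changes. The verbs fit as well: values are analysed against baseline but compared between patients, and the methods sentence says how variables will be compared. On that reading the unpaired t test is applied to change scores in two independent groups. Baseline is used and the test is correct.

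This stands as far as the between-arm comparison goes. It does not settle the rest. Section 16.63 still says that "2D and 3D strain parameters will be analyzed after radiotherapy compared to baseline", and on this reading that contrast has no named test at all instead of an unsuitable one. Nor does the section itself say that the change is the analysis variable; the reader has to import that from the goals.

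Three further points are fair. With positive correlation the unpaired before/after test is conservative, so the risk is a missed decline and not a false alarm. The size depends on an r that the documents do not supply. And the analysis is labelled exploratory, is absent from the secondary endpoints in section 16.2, and feeds neither the primary decision nor the stopping rule. All three limit the importance of the point, but they do not remove it.

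**Conclusion.** The point holds in a limited form. Section 16.63 names no suitable test for the within-patient comparison. If the named unpaired test were used there, its standard error would be too large by a factor of 1.41 at r = 0.5 and 1.83 at r = 0.7. Between arms, the named test is valid but the analysis variable and any baseline adjustment are unspecified. At the same correlations ANCOVA would cut the variance to 0.75 to 0.85 of that of change scores, or to 0.75 to 0.51 of that of post-only values. These figures rest on the assumed r and on equal SDs; the power figures also rest on the assumed effect and subset sizes.

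A reader might infer more: that the between-arm standard errors are also wrong, or that baseline is ignored between arms. The documents do not support either. The unpaired t test keeps its 5% level between arms, and goal 2.26 makes a change-score analysis a natural reading. Nor is there a basis for objecting to chi-square between arms, because section 16.63 names no nominal echo outcome and no expected cell counts can be derived.

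Importance is modest. The aim is listed as secondary in the goals but analysed as exploratory, and the consequence is lost power and an open analytic choice.

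**What to change.** Reword section 16.63 so that each comparison has its own method:

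- **Before/after, within patient:** paired t test or Wilcoxon signed-rank test. If any nominal echo variable is compared before and after, use McNemar's test.
- **Between arms:** ANCOVA of the post-radiotherapy value on arm and baseline value, reporting the adjusted difference with its confidence interval.

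Baseline and follow-up echocardiograms are already scheduled, so the cost is a change of analysis-plan wording, with no new data or visits. Section 16.623 can be checked in the same edit: it names paired tests for a quality-of-life comparison between arms, which is the reverse mismatch.
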